7.1.1 Potential drug-induced liver injury IMP discontinuation criteria

Study participants with potential drug-induced liver injury (PDILI) must be assessed to determine if IMP must be discontinued. In addition, all concomitant medications and herbal supplements that are not medically necessary should also be discontinued.

Immediate and permanent discontinuation of IMP is required for study participants with either of the following PDILI criteria:

- ALT or AST $\geq 8 \times \text{ULN}$
- ALT or AST $\geq 3 \times \text{ULN}$ and coexisting total bilirubin $\geq 2 \times \text{ULN}$

Immediate discontinuation of IMP is required for study participants with the following PDILI criterion:

- Study participants with ALT or AST $\geq 3 \times \text{ULN}$ who exhibit temporally associated symptoms of hepatitis or hypersensitivity. Hepatitis symptoms include fatigue, nausea, vomiting, and right upper quadrant pain or tenderness. Hypersensitivity symptoms may include fever (without clear alternative cause), rash, or eosinophilia.

If a nondrug-related cause for the symptoms can be confirmed, these study participants may resume IMP administration after discussion with the responsible UCB Study Physician, but only when the requirements for rechallenge with IMP (as provided in Section 10.6 [Appendix 6]) are met.

Study participants with the PDILI criterion below may be allowed to continue on IMP at the discretion of the Investigator:

- Study participants with ALT or AST $\geq 5 \times \text{ULN}$ and $< 8 \times \text{ULN}$, total bilirubin $< 2 \times \text{ULN}$, and no eosinophilia, with no fever, rash, or symptoms of hepatitis (eg, fatigue, nausea, vomiting, right upper quadrant pain or tenderness).

Evaluation of PDILI must be initiated (as described in Section 10.6 [Appendix 6]), with repeat tests performed in 2 weeks. Upon retest, if ALT or AST values have reduced to $< 5 \times \text{ULN}$, the study participant can continue with the study. However, if ALT or AST values remain $\geq 5 \times \text{ULN}$ and $< 8 \times \text{ULN}$ after retest, IMP should be temporarily withheld, and study participant should undergo a repeat test in 2 weeks. If ALT or AST values remain

$\geq 5 \times \text{ULN}$ even after the second retest, then the study participant should be permanently withdrawn from the study and should be followed for PDILI.

If a study participant is unable to comply with the applicable monitoring schedule, IMP must be discontinued immediately.

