- A summary of the number and percentage of study participants with a given CTCAE grade (0,1,2,3, or 4) based on minimum/maximum post-baseline value by laboratory variable and treatment group. Two separate tables will show results for the ITP (for the SS) and the initial and maintenance treatment period (combined) (for the AMS).
- Shift tables of the number and percentage of study participants experiencing CTCAE grade 0,1,2,3, or 4 values (as applicable) at Baseline to minimum/maximum post-Baseline CTCAE grade, by laboratory variable and treatment group. Two separate tables will show results for the ITP (for the SS) and the initial and maintenance treatment period (combined) (for the AMS).
- By-study participant listings of all laboratory data (including urinalysis) will be provided. These listings will be presented by treatment group and will include: center, study participant identifier, age, sex, race, weight, visit, laboratory variable, result (with abnormal values flagged as “L” or “H” accordingly) and unit.
- A separate listing will be provided for laboratory results classified as Grade 3 or Grade 4 for the SS.

The table for markedly abnormal liver function tests (LFTs) will contain data beyond the CTCAE Grade 3 thresholds outlined in Section 6.10.1 in order to allow for a more thorough review of elevated LFTs. There will be one table which will list the count and percentage of study participants meeting the below criteria at any time during the study:

- AST: >3xUpper Limit of Normal (ULN), >5xULN, >8xULN, >10xULN, >20xULN
- ALT: >3xULN, >5xULN, >8xULN, >10xULN, >20xULN

- AST or ALT: >3xULN, >5xULN, >8xULN, >10xULN, >20xULN
- Bilirubin: >1.5xULN, >2xULN
- ALP: >1.5xULN

For any participant with at least one markedly abnormal LFT (AST >3xULN, ALT >3xULN, bilirubin >3xULN, or ALP >1.5xULN) the New Ratio (nR) will be calculated as the ratio of either maximum ALT or maximum AST (whichever is higher) to ALP, all expressed as multiples of their ULN as follows:

- $nR = [\text{maximum}(\text{ALT/ULN or AST/ULN})]/(\text{ALP/ULN})$

A plot displaying shift in liver function tests from baseline to maximum post-baseline result and a plot showing maximum post-baseline Total Bilirubin versus maximum post-baseline AST and ALT will be provided for the AMS if there are study participants with reported markedly abnormal LFT.

The following definition of potential drug induced liver injuries (pDILI) will be used (all criteria must be met at the same assessment):

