- (AST or ALT \geq 3xULN) and Total Bilirubin \geq 1.5xULN
- (AST or ALT \geq 3xULN) and Total Bilirubin \geq 2xULN

A table for pDILI will be presented by treatment group for study participants with at least one post-Baseline liver laboratory assessment. Number and percentage of study participants meeting laboratory criteria for pDILI for at least 1 visit and reporting at least 1 symptom potentially associated with hepatitis or hypersensitivity according to the Investigator on the pDILI CRF will be presented.

In addition, a table will be produced to summarize potential Hy's Law cases. The following two definitions will be used in that table (all criteria must be met at the same assessment):

- [AST \geq 3xULN or ALT \geq 3xULN] and Total Bilirubin \geq 2xULN in the absence of ALP \geq 2xULN

In case any study participants meeting the potential Hy's Law criteria, a plot displaying time course for serum LFTs will be provided on the AMS.

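### The SAP's pDILI table requires raised bilirubin, so it omits protocol-defined PDILI cases with total bilirubin below 1.5xULN

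*SAP*

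**What the plan says.** SAP 4.5.3.1 opens its definition with "The following definition of potential drug induced liver injuries (pDILI) will be used (all criteria must be met at the same assessment" and lists two combinations. Both need ALT or AST ≥3xULN; one adds total bilirubin ≥1.5xULN and the other ≥2xULN. A table by treatment group follows, and the SAP specifies: "Number and percentage of study participants meeting laboratory criteria for pDILI for at least 1 visit and reporting at least 1 symptom", the symptoms being those the investigator enters on the pDILI CRF.

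Protocol 7.1.1 names four PDILI criteria, and Table 10-3 has a row for each. They are lettered here for reference:

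- **A.** ALT or AST ≥8xULN.
- **B.** ALT or AST ≥3xULN with total bilirubin ≥2xULN.
- **C.** ALT or AST ≥3xULN in participants "who exhibit temporally associated symptoms of hepatitis or hypersensitivity".
- **D.** ALT or AST ≥5 to <8xULN, total bilirubin <2xULN, no symptoms.

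A and B come under the sentence "Immediate and permanent discontinuation of IMP is required for study participants with either of the following PDILI criteria". C requires immediate discontinuation, with a possible restart if a cause other than the drug is confirmed. For D the protocol says: "Study participants with the PDILI criterion below may be allowed to continue on IMP at the discretion of the Investigator", subject to retesting.

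**The concern.** The two documents use one term for two different sets of participants. In the protocol, A and C carry no bilirubin condition and D requires bilirubin below 2xULN. In the SAP, raised bilirubin is the only way in. The second SAP row is nested in the first, so the two rows form a single rule at ≥1.5xULN with a stricter subset.

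The symptom count does not restore C. Whether it is read as a sub-count or as a condition for entry, it applies only to participants who already meet the bilirubin-based laboratory rule. In the protocol, symptoms are a separate route to PDILI.

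Liver function changes are a prespecified safety topic of interest (Protocol 2.3 and 8.3.7). The table labelled pDILI could show no cases while participants had been taken off IMP for PDILI under the protocol.

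**Working it through.** No plan figure needs reproducing; this is a comparison of definitions.

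**Rules compared.** The protocol rule is A or B or C or D, from 7.1.1. The SAP rule is ALT/AST ≥3xULN and total bilirubin ≥1.5xULN at the same assessment.

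| Protocol criterion | Bilirubin condition | Row in SAP table | Counted by SAP rule |
|---|---|---|---|
| A: ≥8xULN | none | no | only if bilirubin ≥1.5xULN |
| B: ≥3xULN with bilirubin | ≥2xULN | yes | always |
| C: ≥3xULN with symptoms | none | no | only if bilirubin ≥1.5xULN |
| D: ≥5 to <8xULN, no symptoms | <2xULN | no | only if bilirubin is 1.5 to <2xULN |

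**Check on a grid.** Take ALT/AST at 2, 3, 4, 5, 7, 8 and 10xULN, bilirubin at 1, 1.4, 1.5, 1.9, 2 and 3xULN, and symptoms yes or no: 7 × 6 × 2 = 84 combinations. The counts show logical overlap only and are not expected patient frequencies.

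- A: 2 × 6 × 2 = 24 combinations; 2 × 4 × 2 = 16 counted, 8 missed.
- B: 6 × 2 × 2 = 24; all 24 counted.
- C: 6 × 6 × 1 = 36; 6 × 4 × 1 = 24 counted, 12 missed.
- D: 2 × 4 × 1 = 8; 2 × 2 × 1 = 4 counted, 4 missed.
- Any protocol criterion: 64 distinct combinations, of which 44 are counted and 20 missed. The misses sum to 8 + 12 + 4 = 24, less 4 that meet both A and C, giving 20.

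All 20 missed combinations have bilirubin below 1.5xULN.

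**Examples.** ALT 10xULN with bilirubin 1.0xULN requires permanent IMP discontinuation under A and is not SAP pDILI. ALT 4xULN with symptoms and bilirubin 1.0xULN requires immediate discontinuation under C and is not SAP pDILI.

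**The reverse.** ALT/AST ≥3 to <5xULN with bilirubin 1.5 to <2xULN and no symptoms is SAP pDILI but meets no protocol criterion (4 combinations on the grid). The SAP count can therefore differ from the protocol count in either direction.

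**Inconsistency inside the protocol.** Table 10-3 adds to D that the value be ≥2xBaseline; 7.1.1 does not. The grid uses the 7.1.1 form. The two forms differ only when Baseline exceeds 5/2 = 2.5xULN. Exclusion criterion 19 removes Screening values ≥3xULN. If Baseline is also below 3xULN, then 2xBaseline is below 6xULN, and only ALT/AST values from 5 to <6xULN are affected.

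**The case against.** The best defence is that Protocol 7.1.1 is a rule for managing treatment and does not define an analysis. That stands in part. A reader might infer that the SAP dropped a protocol-planned analysis and should have declared it in SAP 4.8. The documents do not support this: Protocol section 9 plans no pDILI table, so there was nothing for SAP 4.8 to declare.

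A second defence is that the cases appear elsewhere, and this largely stands:

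- Protocol 10.6 requires every PDILI event to be reported as an adverse event.
- SAP 4.5.2.2 tabulates TEAEs leading to permanent IMP discontinuation.
- SAP 4.5.2.4.8 captures hepatic events by a broad and narrow SMQ search, whatever the investigator's view of causality, and lists them.
- SAP 4.5.3.1 counts ALT/AST >3x, >5x and >8xULN and lists all laboratory data.

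So it would be wrong to infer that these participants vanish from the report. These outputs still do not sort participants by PDILI criterion. The adverse event tables go by coded term, and the liver function table has no symptom information. A participant stopped under C who later restarts need not appear among permanent discontinuations. The liver function table's strict inequalities differ from the protocol's ≥ only at values exactly on a cut-off, which is trivial.

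Third, the CRF is not among the documents. Protocol 10.6.3 ties the additional PDILI information to events that IMP may reasonably have caused. It cannot be confirmed that symptoms are recorded for every participant with ALT/AST ≥3xULN and normal bilirubin. This limits how fully C can be tabulated.

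**Conclusion.** The mismatch is real and its scope is narrow. Three of the four protocol criteria have no row in the SAP table. The participants missed are those meeting A, C or D with bilirubin below 1.5xULN at that assessment. A reader might infer that everyone taken off IMP for PDILI goes uncounted. That is not so: all B cases count, as do A, C and D cases with bilirubin ≥1.5xULN. Nor does D itself require immediate discontinuation, so the problem of participants stopped but not counted lies mainly with A and C, and with D only if the elevation persists.

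The documents give no expected frequency for such cases, so no size in participants can be stated. The table is descriptive, and no hypothesis test depends on it.

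The conclusion assumes that coexisting bilirubin in criterion B means the same assessment, and that the qualifying values come from the central laboratory, since SAP 4.5.3.1 uses only those in tables. No view is taken on which clinical threshold is right. The change is worth making because the label invites readers to take the count as the protocol's PDILI cases, which it is not.

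**What to change.** In SAP 4.5.3.1:

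1. Keep the two existing rows and label them as a bilirubin-based subset.
2. Add one descriptive row for each protocol PDILI criterion (A to D) and one for any protocol PDILI criterion.
3. Show symptoms from the pDILI CRF as a sub-count, and use them to define row C where they are recorded. State in a footnote if the CRF does not collect them for participants without raised bilirubin.
4. Before programming row D, reconcile Protocol 7.1.1 with Table 10-3 on the ≥2xBaseline condition.

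The cost is a short SAP text change, a few extra rows in a descriptive safety table, and a check of what the pDILI CRF collects. Rows A, B and the laboratory part of D use data already planned for the tables; only the symptom information depends on the CRF.

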4.5.3.2 Vital signs

The following vital signs variables should be summarized: systolic blood pressure (mmHg), diastolic blood pressure (mmHg), body temperature (°C) and heart rate (beats/min). The following analyses will be provided:

For summaries for the ITP and Initial and Maintenance Period (combined) where multiple measurements across different visits are considered (as of markedly abnormal values tables), the vital sign results will be attributed according to their collection date and time at risk for each period (see Section 4.5.1).

- A summary of the absolute and change from Baseline value for each vital sign variable by treatment group and visit for the SS displaying the Placebo/BKZ 320mg Q4W and BKZ 320mg Q4W/Q8W.

- A summary of the number and percentage of study participants experiencing at least one markedly abnormal value for a vital sign variable as defined in Section 6.10.2, by treatment group. Two separate tables will show results for the ITP (for the SS) and the initial and maintenance treatment period (combined) (for the AMS).
- A by-study participant listing of all vital signs data will be provided for the SS. This listing should be presented by treatment group and will include: center, study participant identifier, age, sex, race, weight, visit, vital sign variable and result.

4.5.3.3 Electrocardiograms

Electrocardiogram (ECG) data will be recorded at the Screening Visit. A by-study participant listing of all ECG data will be provided for the SS.

4.5.3.4 Other safety endpoints

4.5.3.4.1 Physical examination

A physical examination is performed at screening, Baseline, Week 16, Week 32/PEOT and SFU and may also be performed at unscheduled visits, although findings are only recorded on the CRF at screening visit. Abnormal results of the physical examination at screening visit together with details of abnormalities: abnormality clinically significant or not, will be listed by study participant for the SS. A by-study participant listing of body weight will also be provided for the SS.

4.5.3.4.2 Assessment and management of TB and TB risk factors

A summary of the number and percentage of study participants with negative, positive, and indeterminate IGRA results at all applicable visits will be presented for the Initial and Maintenance Treatment Period (combined) for the SS presenting Placebo/BKZ 320mg Q4W and BKZ 320mg Q4W/Q8W.

A by-study participant listing of the “Evaluation of signs and symptoms of tuberculosis” questionnaire data and IGRA results will be provided by treatment group for the SS.

A by-study participant listing of the result of study related medical procedures (including chest x-ray and computed tomography) for tuberculosis will be provided by treatment group for the RS.

4.6 Other analyses

4.6.1 Other endpoints and/or parameters

4.6.1.1 Pharmacokinetics

PK variables will be analyzed for all study participants in the PK-PPS. Bimekizumab plasma concentrations will be summarized for each treatment group at each scheduled visit. All plasma concentration data will be reported in µg/mL in the tables, figures, and listings. For study participants randomized to placebo and switched to BKZ 320mg Q4W, the baseline corresponds to the Week 16 pre-dose observation.

PK summaries will be based on observed values. No imputation will be used. However, if plasma concentration measurements are below limit of quantification (BLQ), then for calculation of the derived statistics the result will be set to 0.125 µg/ml, which is ½ of the lower limit of

quantification (LLOQ). Descriptive statistics including number of values, geometric mean, geometric coefficient of variation, geometric mean 95% CI, mean, SD, median, minimum, and maximum if applicable will be calculated if at least $\frac{2}{3}$ of the values of interest are above the LLOQ and $n \geq 3$. Otherwise, only number of values, median, minimum, and maximum will be presented.

If the dosing for a visit is ± 21 days out of window, then the plasma concentration from that visit and all subsequent visits will be excluded from the PK summary.

If the PK sampling date is >1 day after the dosing date, data points will be excluded from the PK summary tables and figures, but not from the listing.

However, all PK concentrations will be listed for the AMS.

If more than 10% of the PK concentration results have been excluded from the table summaries, the PK excluded results will be listed in a separate listing.

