1.3 Schedule of Activities

Table 1-1: Schedule of Activities

Visit ^a / Week	Screening	Initial Treatment Period (weeks after first dose)							Maintenance Treatment Period (weeks after first dose)				SFU ^b
		Baseline (first dose)	1	2	4	8	12	16	20	24	28	32/ PEOT	
Protocol activity													
Informed consent	X												
Inclusion/exclusion	X	X											
Urine drug screen	X												
Demographic data	X												
Psoriasis history	X												
Significant past medical history and concomitant diseases	X	X ^{c,d}											
DLQI		X			X			X	X	X		X	
PSD (P-SIM)													
Physical exam ^e	X	X						X				X	X
Height		X											
Body weight	X	X										X	
Vital signs ^f	X	X			X			X	X			X	X
Hematology and biochemistry	X	X			X			X	X	X		X	X

Table 1-1: Schedule of Activities

Protocol activity	Visit ^a / Week	Screening	Initial Treatment Period (weeks after first dose)						Maintenance Treatment Period (weeks after first dose)				SFU ^b	
			Baseline (first dose)	1	2	4	8	12	16	20	24	28		32/ PEOT
Urinalysis		X	X						X				X	X
ECG		X												
Pregnancy testing ^g		X	X	X	X	X	X	X	X	X	X	X	X	X
Hepatitis B and C testing ^h		X												
HIV testing ⁱ		X												
Chest x-ray/CT scan ^j		X												
IGRA TB test		X										X		
TB questionnaire		X	X						X			X	X	
Blood sample for BKZ plasma concentration			X	X			X		X		X		X	
Blood sample for anti-BKZ antibodies			X				X		X		X		X	X
PASI		X	X	X	X	X	X	X	X	X	X	X	X	
IGA		X	X	X	X	X	X	X	X	X	X	X	X	
Percentage of BSA		X	X	X	X	X	X	X	X	X	X	X	X	
Scalp IGA ^k			X	X	X	X	X	X	X				X	
Concomitant medication		X	X	X	X	X	X	X	X	X	X	X	X	X

Table 1-1: Schedule of Activities

Protocol activity	Visit ^a / Week	Screening	Initial Treatment Period (weeks after first dose)						Maintenance Treatment Period (weeks after first dose)				SFU ^b	
			Baseline (first dose)	1	2	4	8	12	16	20	24	28		32/ PEOT
AEs/ADE and device deficiency assessment		X	X	X	X	X	X	X	X	X	X	X	X	X
IRT ^l		X	X	X	X	X	X	X	X	X	X	X	X	X
BKZ or placebo administration ^{m,n}			X			X	X	X	X	X	X	X		

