Ab=antibody; ADE=adverse device effect; AE=adverse event; BKZ=bimekizumab; BSA=body surface area; CT=computed axial tomography; DLQI=Dermatology Life Quality Index; ECG=electrocardiogram; eCRF=electronic Case Report Form; HBcAb=anti-hepatitis B core antibody; HBsAg=hepatitis B surface antigen; HBV=hepatitis B virus; HCV=hepatitis C virus; HIV=human immunodeficiency virus; IGA=Investigator's Global Assessment; IGRA=interferon-gamma release assay; IMP=investigational medicinal product; IRT=interactive response technology; P-SIM=Psoriasis Symptom and Impact Measure; PASI=Psoriasis Area and Severity Index; PEOT=Premature End of Treatment; PSD=Patient Symptom Diary; Q4W=every 4 weeks; Q8W=every 8 weeks; scalp IGA=scalp-specific IGA; SFU=Safety Follow-Up; TB=tuberculosis

Note: All assessments should be performed prior to IMP administration. The IMP administration is the starting point for the next administration period. Thus, the assessments in Week 16 and Week 32 belong to the previous treatment period.

^a For visits from the first dose of IMP through Week 32, the visit window is ± 4 days from the scheduled visit. For the SFU Visit, the visit window is ± 7 days from the scheduled visit.

^b The SFU Visit will occur 17 weeks after the final dose of IMP.

^c Ensure no significant changes in medical history.

^d Includes evaluation of signs and symptoms of active TB and risk for exposure to TB.

^e The physical examination will be performed as described in Section 8.2.3.

^f Vital signs (sitting systolic and diastolic blood pressure, pulse rate, and body temperature) are to be measured prior to blood sampling and prior to dosing, where applicable.

^g Pregnancy testing will consist of serum testing at Screening. A urine pregnancy test will be administered at all other visits.

^h Study participants who have evidence of or test positive for hepatitis B or C are excluded from the study, per Exclusion Criterion #9 (Section 5.2). A positive test for HBV is defined as: 1) positive for HBsAg or 2) positive for HBcAb. A positive test for HCV is defined as: 1) positive for anti-HCV Ab and 2) positive via a confirmatory test for HCV (eg, HCV polymerase chain reaction).

ⁱ The HIV test results will not be recorded in the eCRF.

^j Screening chest x-ray/CT scan must occur within 3 months prior to Screening Visit.

Table 1-1: Schedule of Activities

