Protocol activity	Visit ^a / Week	Screening	Initial Treatment Period (weeks after first dose)						Maintenance Treatment Period (weeks after first dose)				SFU ^b
			Baseline (first dose)	1	2	4	8	12	16	20	24	28	32/ PEOT

^k The scalp IGA will be assessed for all study participants at Baseline. The scalp IGA will only be assessed at post-Baseline visits for those study participants with scalp involvement (scalp IGA score >0) at Baseline.

^l Investigational medicinal product administration is based on randomization.

^m To protect the blinding of the dosing regimen during the Maintenance Treatment Period, study participants receiving bimekizumab 320mg Q8W will also receive placebo injections at visits in between dosing so that all participants receive injections Q4W.

ⁿ After a study participant completes the Week 16 assessments, which are the last assessments of the Initial Treatment Period, the dose of IMP for the Maintenance Treatment Period will be administered according to the randomization scheme. The final assessments of the Maintenance Treatment Period will be performed at Week 32. No IMP will be administered at Week 32.

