8.6 Pharmacokinetics

Blood samples will be collected prior to dosing for measurement of plasma concentrations of bimekizumab at the visits specified in the SoA (Table 1-1).

Instructions for the collection and handling of biological samples will be provided by the Sponsor. The actual date and time (24-hour clock time) of each sample will be recorded.

Samples will be used to evaluate the PK of bimekizumab. Samples collected for analyses of bimekizumab plasma concentration may also be used to evaluate safety or efficacy aspects related to concerns arising during or after the study.

Study participant confidentiality will be maintained. At visits during which blood samples for the determination of plasma concentrations of bimekizumab will be taken, 1 sample of sufficient volume can be used.

Drug concentration information that may unblind the study will not be reported to any blinded study personnel as long as the study remains blinded.

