4.1.2 Definition of baseline values

A Baseline value for a study participant is defined as the latest measurement for that study participant up to and including the day of first IMP administration, unless otherwise stated. If a Baseline assessment is taken on the same day as first IMP administration, it is eligible to be used as the Baseline value, even in the case that the time of the assessment is recorded as taking place after the time of first IMP administration. This is considered acceptable as this measurement is still the best representation of the Baseline value of the given assessment since it is highly unlikely that the IMP could have an impact on any measurement in such a short period of time. However, such cases should be rare as study center personnel are instructed to do all assessments at the Baseline visit prior to administering IMP. One exception to this rule is plasma concentration. If Baseline plasma concentration is measured at a time after the first IMP administration, then it should not be eligible to be considered as a Baseline plasma concentration. Such cases should be discussed with the quantitative clinical pharmacologist. If a Baseline measurement is missing or not collected, and a Screening value is available, the Screening value will be utilized as Baseline instead.

Baseline values for component scores should be computed using components from the same visit where the relevant measurements were recorded prior to dosing. For example, if the component scores on the Baseline visit cannot be derived due to missing components, the Baseline value for the component score should be calculated using the Screening visit values if the Screening visit has all of the components.

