4.6.1.4 Immunogenicity

4.6.1.4.1 Definitions

4.6.1.4.1.1 ADAb sample status (positive, negative, missing)

The ADAb sample results will be provided as “Positive Screen” (PS) or “Negative Screen” (NS). For samples presenting ADAb levels that are PS, a further confirmatory assay will be performed, and the result will be reported as either “Positive Immunodepletion” (PI) or “Negative Immunodepletion” (NI).

The ADAb status for each sample will be derived as follows:

- Sample values that are either NS, or PS and NI and where the bimekizumab concentration is less than the validated ADAb assay drug tolerance limit ($200\mu\text{g/mL}$) will be defined as ADAb-negative. Since the bimekizumab concentration is not collected at the SFU visit, the ADAb status will be defined as ADAb-negative if the ADAb sample values are either NS, or PS and NI at the SFU visit.
- Sample values that are either NS, or PS and NI and where the bimekizumab concentration exceeded the validated ADAb assay drug tolerance limit will be defined as inconclusive. Since the bimekizumab concentration is not collected at the SFU visit, the ADAb status will be defined as ADAb-negative if the ADAb sample values are either NS, or PS and NI at the SFU visit.
- Sample values that are PS and PI will be defined as ADAb-positive (regardless of availability of a titer value).
- Missing or non-evaluable samples will be defined as missing.

The PI samples will be titrated and the ADA_b titer (reciprocal dilution factor including minimum required dilution) will be reported. The PI samples will also be analyzed in a neutralizing assay to evaluate the anti-bimekizumab antibody neutralized target binding of bimekizumab (IL-17AA or IL-17FF or both) in vitro.

4.6.1.4.1.2 Cumulative ADA_b status

The ADA_b status (positive, negative, or missing) will be considered in a cumulative manner at each time point.

A study participant will be counted positive from the first visit at which the study participant achieved a positive ADA_b sample result to the end of the treatment period, regardless of any missing/inconclusive or negative ADA_b sample result.

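### The PK exclusion rule works on calendar dates, so mistimed post-dose samples stay in the Week 8, 16 and 24 summaries, and it does not say how it applies at Weeks 1 and 32

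*SAP*

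**What the plan says.** Protocol 8.6 fixes the intended timing: "Blood samples will be collected prior to dosing for measurement of plasma concentrations of bimekizumab". The note under Protocol Table 1-1 says the same of every procedure: "All assessments should be performed prior to IMP administration". Protocol 8.6 adds that "The actual date and time (24-hour clock time) of each sample will be recorded".

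SAP 4.6.1.1 summarizes concentrations by treatment group at each scheduled visit, with this screen: "If the PK sampling date is >1 day after the dosing date, data points will be excluded from the PK summary tables and figures". Such points remain in the listing. The same section takes the Week 16 pre-dose value as PK baseline for participants who switch from placebo.

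SAP 4.1.2 has a stricter rule for the first dose only: "If Baseline plasma concentration is measured at a time after the first IMP administration, then it should not be eligible" as a Baseline concentration.

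In Table 1-1, the row "Blood sample for BKZ plasma concentration" marks Baseline and Weeks 1, 8, 16, 24 and 32. SAP 6.11 lists the dosing visits as Baseline and Weeks 4, 8, 12, 16, 20, 24 and 28. Table 1-1 confirms that "No IMP will be administered at Week 32".

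**The concern.** The design calls for pre-dose samples, but the screen tolerates post-dose ones. It compares dates rather than times and allows a further day. A sample taken an hour after the injection has a date difference of 0, and one taken the next day a difference of 1; neither exceeds 1. The SAP recognises the problem at Baseline, but its safeguard is tied to the first IMP administration. For the placebo arm that dose is placebo, so the safeguard does not reach Week 16, their first active dose.

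Separately, *the dosing date* is not defined. PK is sampled at two visits without a dose, so a programmer has to decide what the rule means there. The corresponding rule for antibody samples (SAP 4.6.1.4.1.7) treats Week 32, PEOT and SFU separately; the PK rule has no such clause.

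At stake are the by-visit concentration summaries and the tables and figures of concentration by ADAb and NAb status (SAP 4.6.1.4.2.2). Protocol 2.3 says that no Chinese participants contributed data to the completed global pivotal program, so these summaries describe exposure in a population not previously covered.

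**Working it through.** **Step 1. PK visits against doses.** Sampling visits are read from the column positions in Table 1-1. The absence of an SFU sample agrees with SAP 4.6.1.4.1: "Since the bimekizumab concentration is not collected at the SFU visit". Check on the dosing visits: 8 visits × 2 injections = 16, the total given in SAP 6.11.

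| PK visit | Dose at visit? | Nominal days since previous injection | If *the dosing date* is this visit's dose | If it is the previous dose |
|---|---|---|---|---|
| Week 1 | no | 7 | undefined, nothing dropped | dropped |
| Week 8 | yes | 28 | kept up to +1 day | dropped |
| Week 16 | yes | 28 | kept up to +1 day | dropped |
| Week 24 | yes | 28 (56 since active, Q8W arm) | kept up to +1 day | dropped |
| Week 32 | no | 28 (56 since active, Q8W arm) | undefined, nothing dropped | dropped |

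The ±4-day visit windows change nothing: the gap is 7 ± 4 = 3 to 11 days at Week 1 and 28 ± 8 = 20 to 36 days at Week 32, always above 1. The previous-dose reading removes every post-Baseline sample, so it cannot be meant. The same-visit reading is the workable one, and it admits post-dose samples at Weeks 8, 16 and 24.

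**Step 2. Effect of one late sample.** The documents give no PK parameters. Assume one compartment with first-order absorption, elimination half-life 14 to 28 days and absorption half-life 1 to 5 days. With doses at times d,

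C(t) ∝ Σ [ka/(ka − ke)] · [exp(−ke(t − d)) − exp(−ka(t − d))], ke = ln 2 / elimination half-life, ka = ln 2 / absorption half-life.

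R is the concentration one day after the visit's dose divided by the pre-dose concentration.

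Worked case, Week 24 in the Q8W arm, half-lives 14 days and 1 day. Active doses at Weeks 0, 4, 8, 12 and 16 lie 168, 140, 112, 84 and 56 days back. The factor ka/(ka − ke) cancels in R, and the absorption terms of the old doses are negligible.
- Pre-dose: 2⁻¹² + 2⁻¹⁰ + 2⁻⁸ + 2⁻⁶ + 2⁻⁴ = 0.0833.
- One day later: 0.0833 × 2^(−1/14) + (2^(−1/14) − 2⁻¹) = 0.0792 + 0.4517 = 0.5309.
- R = 0.5309 / 0.0833 = 6.4.

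Over the whole grid:

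| Visit | R, sample one day late |
|---|---|
| Week 8 | 1.12 to 2.40 |
| Week 16 | 1.09 to 2.31 |
| Week 24, Q8W arm | 1.19 to 6.38 |
| Week 24, placebo switchers on Q4W | 1.12 to 2.40 |

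**Step 3. Effect on the reported geometric mean.** If a fraction f of samples is one day late, the geometric mean is multiplied by R^f. With f = 10% (an assumption):
- Weeks 8 and 16: 1.09^0.1 = 1.009 to 2.40^0.1 = 1.09, a rise of about 1% to 9%.
- Week 24, Q8W arm: 1.19^0.1 = 1.018 to 6.38^0.1 = 1.20, a rise of about 2% to 20%.

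**Step 4. Placebo switchers at Week 16.** Having had no active drug, they should be below quantification, that is below 0.25 µg/mL (twice the 0.125 µg/mL substituted under SAP 4.6.1.1). With an assumed V/F of 8 to 14 L, ka of 0.2 to 0.5 per day and half-life of 20 to 28 days, one 320 mg dose gives about 4 to 16 µg/mL after 24 hours. The SAP reports only n, median, minimum and maximum when fewer than two thirds of values are above the LLOQ, so a few such samples would show in the maximum and not move the median.

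**The case against.** The strongest reply is that the protocol requires pre-dose sampling twice and IMP is given in the clinic, so post-dose samples are protocol breaches and should be few. That stands: the rule does not turn the summary into something other than a pre-dose summary; it fails to remove exceptions.

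A full day's delay is also the worst case the rule admits. On the same grid, a sample two hours late gives R of 1.01 to 1.16 at Weeks 8 and 16, and 1.02 to 1.62 at Week 24 in the Q8W arm. That also stands.

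It can be said that the switchers' baseline is already defined as pre-dose. True for the baseline definition, but the by-visit Week 16 summary is governed by the date rule, which does not enforce that definition.

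The PK-PPS excludes participants with important deviations affecting concentration. The deviation criteria sit in a separate document, so this may catch some cases; nothing here shows that it does.

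A reader might infer that the rule discards Weeks 1 and 32, two of five post-Baseline time points. That needs a mixed reading: same-visit dose where there is one, otherwise the previous dose. The SAP contradicts it. It summarizes every scheduled visit, shows concentrations by ADAb and NAb status up to Week 32 (4.6.1.4.2.2), and forms trough tertiles for TEAEs from Week 32 samples (4.5.2.2).

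**Conclusion.** The point holds as a gap in a stated rule. At Weeks 8, 16 and 24 the screen leaves in samples taken up to a day after the injection, contrary to the sampling design and to the SAP's own treatment of Baseline. At Weeks 1 and 32/PEOT it is ambiguous; this is not a planned loss of data.

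Two further inferences should be resisted. The summaries are not generally a mixture of post-dose and pre-dose values, because only mistimed samples are affected and the documents do not allow their number to be computed. And the Week 32 trough tertiles cannot be distorted by a same-visit dose, since none is given.

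The sizes above (geometric mean up by 1% to 9%, or 2% to 20% at Week 24 in the Q8W arm) rest on assumed kinetics and an assumed 10% of samples a full day late. PK is a tertiary, descriptive endpoint; the co-primary and key secondary tests are untouched. This is an inexpensive improvement.

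**What to change.** Amend SAP 4.6.1.1 as follows:
- Define *the dosing date* as the date and time of the injection at the same visit.
- At dosing visits, exclude from PK tables and figures any sample whose recorded date and time fall after that visit's injection. Apply the same test to the Week 16 baseline of placebo switchers and to the tables and figures by ADAb and NAb status.
- State that the rule does not apply at Weeks 1 and 32/PEOT, where samples are included by visit window.

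Sample times are already recorded under Protocol 8.6, and SAP 4.1.1.2 and 4.1.2 already rely on the time of IMP administration. The cost is a few lines of SAP text and one date/time comparison in the PK program. The downside is that a few mistimed samples appear in listings only.
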